### ***Sessions 3-5: Overview of Session Protocol for CBST Sessions***

Each of the three CBST sessions follows a similar protocol, although a different module/s may be covered in each session. Although modules are general guidelines for delivering skills, content covered with the participant should be specific to the participant’s needs. The therapist should *try to complete at least two modules for each target behavior* (substance use / medication adherence). More than one module may be presented to the participant during a single session, but it is important that the participant doesn’t become overwhelmed by information. ***With permission, teach coping skills, conduct in-session exercise, and assign practice exercise.***

### ***Session 6: Overview of Relapse Prevention Protocol***

Initial step of this session is to *briefly review the goals previously identified* in the change plan. This summary should acknowledge ongoing discrepancy between current and desired status; however, it should also incorporate an *emphasis on progress made* during treatment. If the participant is in action or maintenance phase, the therapist needs to assess the participant’s interest and willingness to discuss a *relapse prevention plan*. The therapist also needs to collaborate with the participant to develop an *emergency plan* on how they might cope with a high risk situation and what they would do should a slip or relapse occur.

### ***Booster Session:***

The purpose of the optional booster session was to ‘check in’ with the participant on how they are doing with their drinking, substance use and HIV medication adherence, and remind them of when their next booster is (except for when this is the final booster session). At the end of the

session, summarize the main points affirming any efforts the participant has made to proceed towards their goals. Briefly recap any plans made during the session, including any plans to access referrals.

### **Timeline**

The PLUS intervention was adapted from an original eight session intervention to six sessions based on feedback from mental health staff at the sites. c. Research staff will keep track of participant's attendance during PLUS intervention period via the tracking log. Booster sessions will also be scheduled and conducted but will not be required for treatment exposure to the PLUS intervention.

### **Enrollment in Immediate and Waitlist control conditions**

Potential participants in the immediate and waitlist control conditions were identified through a prescreening review of EMR, which provided study staff members with lists of patients with scheduled clinic visits who had one or more detectable viral load within the past year. Study staff approached these patients during clinic visits to introduce PLUS and invited them to participate in screening. Participants provided verbal consent for screening and provided written informed consent if they were eligible and interested in enrolling. They also granted permission for the study team to abstract their EMR data for study screening and enrollment purposes.

Once consent to use the EMR was granted, eligibility criteria were verified for ART regimen and viral load. Participant self-report was used to determine alcohol and substance use criteria on the screening questionnaire. Eligible participants who enrolled in the study were scheduled for a baseline visit, which could take place the same day post-screening or be scheduled within the ensuing month. The full protocol was approved by the institutional review boards at Hunter College and Mt Sinai.

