## **Selection of No Treatment control patients**

The EMRs of randomly selected patients who belonged to the TAU site and were not enrolled in the PLUS trial were matched on key patient characteristics for comparisons with EMRs of patients in the PLUS intervention and Waitlist control conditions. This matched cohort of patients received care at a fourth clinic that did not receive any intervention (i.e., PLUS or eTAU) and was considered as a natural history comparison group. We generated a pool of patient records from which to randomly select the TAU matched cohort of patients ( $n = 120$ ). We included patient records of patients with an HIV diagnosis who had at least 1 primary care visit at the TAU clinic, received ART, and had a viral load (VL)  $>200$  copies/mL during the PLUS enrollment period from March 26, 2015 to March 16, 2017. EMRs of 20 patients who were enrolled in PLUS and possibly transferred to receive HIV care at the TAU clinic during the study period were excluded. Additionally, records of 9 patients with only one primary care visit and no follow-up visits during the study period were excluded from the pool of patient records.

Case control matching using the pool of patients meeting the criteria described above allowed us to randomly select the TAU cohort of 120 patients while matching as closely as possible to patients enrolled in the trial on key variables: age group (with ranges 18-29, 30-39, 40-49, and 50 or older), racial and ethnic identity (Black, Hispanic/Latinx, White, Asian/Pacific Island, Other/Multiracial), and gender (recorded as male or female). Additionally, we matched on indicators of substance misuse based on EMRs of trial participants using documentation of substance use problems or ICD-10 diagnostic codes, such as documentation of alcohol abuse or dependence, having had a substance use diagnosis, or any indication of substance misuse during the study period. EMRs were then extracted for the TAU cohort of patients similar to the records

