for the trial participants. A de-identified dataset was generated linking all patient EMRs to an unique study ID number with the following variables: demographic variables, HIV diagnosis, HIV clinical outcomes, ARV regimen, ICD-10 diagnoses of AIDS defining illness, substance use disorders, psychiatric disorders, non-AIDS defining infections (bacterial pneumonia, cellulitis, sepsis), cardiovascular, gastrointestinal, liver, kidney, pulmonary, endocrine, immune, and oncologic diseases, as well as sexually transmitted infections. In addition, records about services received and type of outpatient clinic visits were extracted, such as whether the visit was an HIV primary care visit, a specialty or non-HIV primary care visit type (dentist, OB/GYN, hematology), mental health visit, and substance use visit.

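### In the viral load and CD4 models, trial enrolment may be confounded with prior engagement in care relative to the EMR referent, and the extracted visit records are not used to check or adjust for it

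*Combined protocol and SAP*

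**What the plan says.** **Entry to the trial** (Enrollment in Immediate and Waitlist control conditions). One route served both trial conditions: "Potential participants in the immediate and waitlist control conditions were identified through a prescreening review of EMR". The review produced "lists of patients with scheduled clinic visits who had one or more detectable viral load within the past year", and then "Study staff approached these patients during clinic visits to introduce PLUS and invited them to participate in screening".

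**Entry to the EMR cohort** (Selection of No Treatment control patients). "We generated a pool of patient records from which to randomly select the TAU matched cohort of patients". The pool required at least one primary care visit at that clinic, ART, and a VL above 200 copies/mL in the enrolment period. In addition, "records of 9 patients with only one primary care visit and no follow-up visits during the study period were excluded from the pool". No such exclusion is stated for trial participants. Then: "Case control matching using the pool of patients meeting the criteria described above allowed us to randomly select the TAU cohort of 120 patients". The matching variables were age group, race/ethnicity, gender and indicators of substance misuse.

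**Data available.** The same section states that "records about services received and type of outpatient clinic visits were extracted", with HIV primary care, specialty, mental health and substance use visits distinguished.

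**Analysis** (Data Analysis Plan). The match is checked on age, race/ethnicity and gender. The VL and CD4 models adjust for the baseline value of the outcome and for gender. Clinic and condition enter as a four-category dummy-coded predictor. In the VL and CD4 models only, the EMR cohort is added as a further subgroup and is the referent.

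**The concern.** A patient at Sites 1 to 3 could be approached only when attending, so the chance of entry should rise with the number of visits kept. Those who consented also accepted repeated on-site assessments. Controls were sampled by patient, not by visit. If patients who attend more differ in later VL or CD4 for reasons unrelated to PLUS, every planned coefficient against the EMR referent absorbs part of that difference.

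VL and CD4 are listed as primary outcomes. After month 12 the waitlist participants receive PLUS, so the EMR cohort is the only untreated comparator left for Slope 2. The plan extracts the data that could show whether the groups differ in attendance, but assigns them no role in the match, its check or the models.

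**Working it through.** The documents give no visit counts, approach rates, group sizes by site, or power calculation, so there is no stated figure to reproduce. The check has a documentary part and an illustrative part.

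**1. Where visit information is used**

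| Step | Variables | Visit variable? |
|---|---|---|
| Trial recruitment | scheduled-visit list, approach at visit | yes, implicitly |
| Control pool | at least 1 primary care visit; 9 patients removed | as a floor only |
| Matching | age group, race/ethnicity, gender, misuse | no |
| Check of match | age, race/ethnicity, gender | no |
| VL/CD4 covariates | baseline outcome, gender | no |

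**2. What the controls-only exclusion can do.** The pool had to hold at least 120 patients after exclusions, so the 9 removed were at most 9/(120 + 9) = 7.0% of it. The exclusion cannot balance attendance above one visit. It also conditions on later follow-up in one group only.

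**3. Size of the visit gap (all inputs assumed).** The enrolment window, 26 March 2015 to 16 March 2017, is 721 days. Assume visits v per patient are negative binomial with mean 6, 8 or 12 and shape 1.5 or 3, truncated at v ≥ 1. Let p be the chance per visit of being approached and enrolled; then P(enrol | v) = 1 − (1 − p)^v. Controls are one draw per patient with v ≥ 2. Gap = (mean visits of enrolled − mean visits of controls) / SD of controls.

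| p | Gap, SD |
|---|---|
| 0.02 | 0.52 to 0.63 |
| 0.10 | 0.28 to 0.36 |
| 0.30 | 0.07 to 0.11 |
| 0.60 | −0.06 to 0.00 |

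Example (mean 8, shape 3, p = 0.10): (10.24 − 8.50)/5.23 = 0.33. Three of the six visit distributions put more than 7.0% of patients at a single visit, above the ceiling in step 2. Without them the rows become 0.52 to 0.62, 0.28 to 0.33, 0.07 to 0.10 and −0.02 to 0.00, so the reading is the same.

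**4. What a gap could do to a test (scenario only).** Bias = gap × r, where r is an assumed correlation of engagement with the outcome after baseline adjustment. With no PLUS effect, the two-sided 5% test rejects with probability Φ(b/SE − 1.96) + Φ(−b/SE − 1.96).

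The model estimates one coefficient per site/condition. Assuming four equal groups, 174/4 = 43.5, SE = √(1/43.5 + 1/120) = 0.177 SD:

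| Gap | r = 0.1 | r = 0.2 | r = 0.3 |
|---|---|---|---|
| 0.1 | 5.0% | 5.1% | 5.3% |
| 0.25 | 5.2% | 5.9% | 7.1% |
| 0.4 | 5.6% | 7.4% | 10.4% |

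Pooling all 174 against 120 gives SE = √(1/174 + 1/120) = 0.119. Biases of 0.06 and 0.12 SD then give 8.0% and 17.3%. The plan does not specify that pooled contrast for the outcomes; 174 versus 120 is the check of the match, and the 174 include waitlist participants.

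**The case against.** **Scope.** A reader might infer that engagement is confounded with PLUS itself. The documents do not support that. Waitlist participants were recruited by the same route and did not receive PLUS until after month 12, so immediate-versus-waitlist contrasts up to then are free of this mechanism. The EMR cohort does not enter the AUDIT, adherence or DAST models. The waitlist-versus-EMR coefficient through month 12 even offers a partial internal check, since neither group had PLUS, although it also carries clinic differences. This objection stands and limits the point to VL and CD4 against the EMR referent.

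**Direction.** A reader might also infer that the bias favours PLUS. That is not shown. Among patients on ART with VL above 200, frequent attendance may mark harder-to-treat disease, and the controls-only exclusion enriches the controls for retention. Both could work the other way.

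**Size.** A per-visit chance of 0.3 or more makes the gap small, and near-saturated recruitment removes it. The calculation treats each visit as a fresh chance to enrol, which is a simplification. Baseline adjustment removes some of any bias.

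**The control draw is not wholly blind to attendance.** A recorded VL above 200 and documented misuse during the study period are both likelier in patients who attend more. This narrows the asymmetry but does not balance visit frequency.

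None of this answers the core: recruitment was visit-based on one side and per patient on the other, and no step checks or adjusts for attendance.

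**Conclusion.** The point holds in limited form. In the VL and CD4 models, trial enrolment may be confounded with prior engagement in care relative to the EMR referent, and the plan neither checks nor adjusts for it. The difference in sampling and the absence of visit variables are documented. Over-sampling of frequent attenders is an inference from the sampling route, sound unless recruitment came close to saturation.

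Size and direction are unknown. The visit gap runs from about 0 to 0.4 SD or more, depending entirely on assumed visit and approach rates. No single inflated error rate should be quoted as a finding: the 8% to 17% figures need both the upper part of the assumed range and a pooled contrast that the plan does not specify, while the same biases give about 6% to 10% for one group of about 43, itself an assumed size. The case for acting is that a primary-outcome contrast has an uncorrected selection difference which extracted data could largely reveal.

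**What to change.** 1. From the extracted records, derive two counts per patient over a fixed period (for example 12 months): kept HIV primary care visits, and mental health or substance use visits. Count back from baseline for trial participants and from the qualifying VL for controls. Use pre-entry visits only, because later attendance may be affected by PLUS.
2. First confirm that the extraction reaches back that far; the plan states no look-back window for visit records and defines no index date for controls.
3. Report the balance of both counts by site/condition and for the EMR cohort, alongside the existing check of the match.
4. Add both counts to the VL and CD4 models as covariates, or use them in weights. As the controls are already selected, this is more practical than rematching.
5. Apply the single-visit/no-follow-up exclusion equally to trial participants and controls, or show results with and without it.
6. State in the plan that this applies to contrasts with the EMR referent only.

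The cost is two extra parameters, a flag for patients with a short history at the clinic, and a few sentences in the Data Analysis Plan. It does not deal with clinic-level differences: the controls all come from Site 4, and attendance covariates leave that confounding in place.

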### **Therapist Training**

All therapists involved in the PLUS intervention were trained on Motivational Interviewing (MI), Cognitive Behavioral Skills Training (CBST), and the PLUS Clinical Manual. MI and CBST trainings were provided by the Center for HIV Educational Studies and Training (CHEST). After trainings, therapists held four mock-sessions with a mock participant. All MI mock sessions were coded via the Motivational Interviewing Treatment Integrity (MITI) system and were reviewed for fidelity with CBST. Therapists were given feedback from trainers

and were asked to repeat session based on feedback to reach competency in intervention as needed.

### **Intervention Monitoring and Quality Control**

Standardized rating systems (MITI Coding with a CBST checklist) were used to evaluate the competency of study therapists prior to rollout of the full trial. Once the trial began, we monitored the implementation and select 25% of taped sessions to assess fidelity to protocol.

## **MEASURES**

### *Primary Outcome Measures*

- Biological Marker of HIV-Related Health Outcomes
  - Viral load and CD4 extracted from EMR
- Alcohol Use
  - Alcohol Use Disorders Identification Test (AUDIT)
  - Hazardous Drinking
- Medication Adherence
  - Visual Analog Scale (VAS) for Medication Adherence

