## **Trial Design**

This study utilized a CET design to evaluate the effectiveness of the PLUS intervention components against a waitlist condition, and for VL and CD4, against a No-Treatment control group. Four sites were distributed across three study conditions in a quasi-experimental design. Two sites (Sites 1 and 2) implemented immediate treatment (Condition 1). Immediately after baseline, participants were offered the PLUS intervention. Participants then completed follow-up assessments at 3, 6, 9, 12, 15 and 18 months post-baseline. Site 3 implemented both the waitlist condition (Condition 2) from March 26, 2015 to October 31, 2016, and an immediate condition. Due to challenges in participant accrual, this site shifted to enrolling participants in the immediate intervention condition from November 1, 2016 through the end of the study. Participants in the waitlist condition received the intervention following completion of their 12-month follow-up. Site 4 is the no-Treatment Control EMR Group.

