### **Data Analysis Plan**

To assess the effectiveness of our randomization procedure, we used chi-square tests and ANOVAs to investigate the equivalence of possible cofounders across each of the PLUS-enrolled four site/conditions at baseline. Specifically, we examined proportional differences across demographic characteristics (race and ethnicity, sexual and gender identity, and education), and mean differences across age and baseline outcome values (alcohol severity, drug use severity, medication adherence, viral load, and CD4). Where cell sizes were too small ( $n < 5$ ) to permit chi-square tests, we utilized a Fisher's exact test, at  $p < .05$ . The matching of the No Treatment control group ( $N = 120$ ) was assessed by bivariate comparisons with the entire PLUS-enrolled sample ( $N = 174$ ) on the available variables of age, race and ethnicity, and gender.

We also conducted analyses to test for the presence of differential attrition between conditions and sites where appropriate. First, we conducted chi-square analyses to test for differential attrition by site and study arm at each follow-up. We also tested for differential attrition at each follow-up across site, as well as several demographic characteristics (race and ethnicity, sexual and gender identity, and education). Finally, we conducted a series of point-biserial correlations to examine attrition at each wave by age and baseline outcome values (alcohol severity, drug use severity, medication adherence, viral load, and CD4).

Outcome analyses were conducted using piece-wise longitudinal growth curve models, adjusting for baseline scores on the corresponding outcome and, for the models predicting medication adherence, AUDIT, and DAST, we also adjusted for gender identity and sexual orientation, whereas for the models predicting viral load and CD4 we adjusted for gender (male, female) as sexual identity was not indicated in the EMR records for the matched cohort. For the

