DAST model, DAST was treated as a count variable having a negative binomial distribution. The latent intercept represented the initial 3-month follow-up time point. Slope 1 quantified linear change across the 3-, 6-, 9- and 12-month follow-ups. Where possible for outcomes variables extracted from EMR (i.e., CD4 count and viral load), Slope 2 quantified changes in trajectory at the 15- and 18-month follow-up corresponding to the point at which the waitlist control condition received the intervention. The fixed effect of clinic and condition was entered as a 4-category predictor that was dummy-coded. For viral load and CD4 models – where data were taken from EMR records – the EMR cohort control participants were included as an additional subgroup and served as the referent category.

All models were estimated using full-information maximum likelihood estimation in MPlus Version 8.0. Good model fit was assumed when the  $\chi^2/df$  ratio was 3 or less, root-mean square error of approximation (RMSEA)  $\leq 0.05$ , Tucker-Lewis fit index (TLI)  $> 0.95$ , and comparative fit index (CFI)  $> 0.95$ .

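### Does the unstated scale for viral load call for a change to the analysis plan?

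*Combined protocol and SAP*

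**What the plan says.** The Primary Outcome Measures list gives viral load in one line: "Viral load and CD4 extracted from EMR". The Data Analysis Plan then states: "Outcome analyses were conducted using piece-wise longitudinal growth curve models, adjusting for baseline scores on the corresponding outcome". For viral load and CD4 the covariate is gender, a second slope covers months 15 and 18, and "the EMR cohort control participants were included as an additional subgroup and served as the referent category". Estimation is by full-information maximum likelihood in Mplus.

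The only outcome given a named distribution is the drug-use score: "DAST was treated as a count variable having a negative binomial distribution". Viral load also enters two preliminary checks. The baseline comparison looks at "mean differences across age and baseline outcome values (alcohol severity, drug use severity, medication adherence, viral load, and CD4", and the attrition analysis uses "a series of point-biserial correlations to examine attrition at each wave by age and baseline outcome values".

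The figure of 200 copies/mL appears in Inclusion Criteria and in the selection of the No Treatment controls, each time as a selection threshold. No section states a transformation, a rule for below-limit values or a suppressed/unsuppressed endpoint.

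**The concern.** Viral load in copies/mL is heavily right-skewed, and a few very high values can carry most of the variance. Everyone enters above 200 copies/mL, so becoming suppressed is a natural route for benefit. A normal-theory model on copies/mL could bury such an effect. The outcome matters here because, under Trial Design, viral load and CD4 are the only outcomes tested "for VL and CD4, against a No-Treatment control group". A null result on the wrong scale would be hard to interpret. It also looks odd that a secondary outcome has its distribution stated and a primary one does not.

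**Working it through.** **1. What the text supports.** The plan states no power, effect size, SD or suppression rate, so there is no figure to reproduce. The first question is whether any sentence implies copies/mL.

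| Text | Fits copies/mL? | Fits log10? |
|---|---|---|
| Baseline mean differences | yes | yes |
| Point-biserial correlations with attrition | yes | yes |
| Growth model adjusted for baseline score | yes | yes |
| Distribution named only for the drug-use score | yes | yes: log10 viral load would be treated as an ordinary continuous outcome |

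None of these separates the two. The outcome list is equally bare for CD4, the AUDIT, hazardous drinking and the adherence scale, so the brevity is general.

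**2. Cost if copies/mL had been used.** From the document: 174 enrolled, 120 record controls, baseline above 200 copies/mL, months 3 to 18 with the intercept at month 3, and a four-category clinic/condition predictor with the record cohort as referent. Equal groups give 174/4 = 43.5, about 44 per group.

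Assumed: an equal or a 29/29/29/87 split (2 options); baseline log10 mean/SD of 3.5/0.7, 3.8/0.8 or 4.2/0.9 (3); person/visit SD of 0.5/0.5, 0.3/0.3 or 0.2/0.3 (3); upper cap of none, 1,000,000 or 100,000 (3); persistent or visit-level suppression (2); floor of 20; no missing data. That is 2 × 3 × 3 × 3 × 2 = 108 settings per effect, with 1,000 replicates each.

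Power for one group v 120 at the month-3 intercept, 30% v 50% suppressed, equal groups:

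| Upper cap | Copies/mL |
|---|---|
| none | 4–9% |
| 1,000,000 | 6–15% |
| 100,000 | 15–40% |

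Log10 gave 53–71% across all caps. Over both splits, copies/mL had less than half the power of log10 in 100 of 108 settings.

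**3. Dependence on the kind of effect.** Settings in which copies/mL matched or beat log10, one group v 120:
- suppression only (30% v 50%): 0 of 108
- mixed (30% v 40% plus a 0.3 log10 shift): 16 of 108
- shift only (0.5 log10): 49 of 108

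Under the null, rejection was 2.5–8.1% on copies/mL and 3.3–7.3% on log10, so no type I error claim is made.

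**4. Simpler cross-check.** A single-visit ANCOVA with 120 v 58 (assumed group size 174/3 = 58) and 30% v 50% suppressed, at SD 0.6/0.8/1.0, gave 11%/5%/3% on copies/mL and 72%/67%/62% on log10. For suppression as a proportion:

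power = Φ[(0.20 − 1.96·SE₀)/SE₁]

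The pooled rate is (36 + 29)/178 = 0.365. SE₀ = √[0.365·0.635·(1/120 + 1/58)] = 0.0770 and SE₁ = √(0.21/120 + 0.25/58) = 0.0778. The result is Φ(0.63) = 0.736, or 74%. The direction agrees with step 2.

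**5. The other two omissions.** With a 1,000,000 cap and equal groups, setting suppressed values at 199 rather than 20 moved log10 power from 54–71% to 43–65%, a smaller effect than the choice of scale. A month-12 suppression test (one group v 120) had 54–66% power for the suppression effect, 25–37% for the mixed effect and 6–20% for the shift-only effect.

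**The case for a change.** The best case for a change is that convention does not tell a reader what was done. The authors named special handling where they used it, a primary outcome deserves at least as much, and a sentence would settle the scale. Leaving it open also leaves several viral load analyses available, with no evidence that one was fixed in advance. Two simulations with different structures agree that copies/mL would be costly for a suppression-driven effect.

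The omission is real and the direction of the simulations stands. The step from silence to error does not. Naming a distribution for one count outcome is what one expects if the other outcomes, including log10 viral load, were treated as continuous. The plan is written in the past tense, so adding a scale now could not restore prespecification. It would be disclosure, which belongs in the report of results. A suppression model would be an additional analysis, and a weak one for mixed or shift-only effects.

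**Conclusion.** No change to the plan follows. The document omits the viral load scale and the below-limit rule, but nothing in it indicates copies/mL, and an analyst would ordinarily take logs and assign a value to below-limit results.

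The possible harm is conditional: 4–40% power against 53–71% for one group v 120, only if copies/mL were modelled and only if the effect works mainly through suppression. It rests on assumed suppression rates, SDs, caps, floor and group split, on complete data, and on least squares applied to person-level coefficients in place of the plan's estimator. For shift-only effects the advantage of log10 is not general. Even on log10, the group-versus-referent contrast that the plan specifies reaches only 53–71%, so a null would be hard to interpret on either scale. What remains is a reporting detail.
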